8.5 Infection Precaution

Everolimus has immunosuppressive properties and may predispose patients to infections, especially those with opportunistic pathogens. Localized and systemic infections, including pneumonia, other bacterial infections and invasive fungal infections, such as aspergillosis, candidiasis, or pneumocystis jirovecii pneumonia (PJP) and viral infections including reactivation of hepatitis B virus, have been described in patients taking everolimus. Some of these infections have been severe (e.g. leading to sepsis; respiratory or hepatic failure) and occasionally have had a fatal outcome. Physicians and patients should be aware of the increased risk of infection with everolimus, be vigilant for symptoms and signs of infection, and institute appropriate treatment promptly.

8.6 Management of Hepatitis Reactivation

In cancer patients with hepatitis B, whether carriers or in chronic state, use of antivirals during anticancer therapy has been shown to reduce the risk of hepatitis B virus (HBV) reactivation and associated HBV morbidity and mortality. (*Lomba et al. 2008*)

**Monitoring and prophylactic treatment for hepatitis B reactivation**

[Table 1](#) provides details of monitoring and prophylactic therapy according to the baseline results of viral load and serologic markers testing.

**Table 1 Action to be taken for positive baseline hepatitis B results**

Test	Result	Result	Result	Result	Result
HBV-DNA	+	+ or -	-	-	-
HBsAg	+ or -	+	-	-	-
HBs Ab	+ or -	+ or -	+	+ or -	- or + with prior HBV
			and no prior HBV		

Test	Result	Result	Result	Result	Result
			vaccination		vaccination
HBc Ab	+ or -	+ or -	+ or -	+	-
Recommendation	Prophylaxis treatment should be started 1-2 weeks prior to first dose of study drug  Monitor HBV-DNA approximately every 4-6 weeks		No prophylaxis  Monitor HBV-DNA approximately every 4-6 weeks		No specific action

Antiviral prophylaxis therapy should continue for at least 4 weeks after last dose of study drug.

For hepatitis B reactivation, definition and management guidelines, see [Table 2](#) Guidelines for management of hepatitis B.

**Table 2 Guidelines for management of hepatitis B**

HBV reactivation (with or without clinical signs and symptoms)*	

For patients with baseline results: Positive HBV-DNA OR positive HBsAg ----- reactivation is defined as: [Increase of 1 log in HBV-DNA relative to baseline HBV-DNA value OR new appearance of measurable HBV-DNA] AND ALT elevation x 5 ULN
	
Treat: Start a second antiviral AND Interrupt study drug administration until resolution: ≤ Grade 1 ALT (or baseline ALT, if > Grade 1) and ≤ baseline HBV-DNA levels  If resolution occurs within ≤ 28 days study drug should be re-started at one dose lower, if available. If the patient is already receiving the lowest dose of study drug according to the protocol, the patient should restart at the same dose after resolution. Both antiviral therapies should continue at least 4 weeks after last dose of study drug.  If resolution occurs > 28 days Patients should discontinue study drug but continue both antiviral therapies at least 4 weeks after last dose of study drug.

For patients with baseline results: Negative HBV-DNA and HBsAg AND [Positive HBs Ab (with no prior history of vaccination against HBV), OR positive HBc Ab] -----
	
Treat: Start first antiviral medication AND Interrupt study drug administration until resolution: ≤ baseline HBV-DNA levels  If resolution occurs within ≤ 28 days study drug should be re-started at one dose lower, if available. If the patient is already receiving the lowest dose of study drug according to the protocol, the patient should restart at the same dose after resolution. Antiviral therapy should continue at least 4 weeks after last dose of study drug.

HBV reactivation (with or without clinical signs and symptoms)*	
reactivation is defined as: New appearance of measurable HBV-DNA	If resolution occurs > 28 days Patients should discontinue study drug but continue antiviral therapy at least 4 weeks after last dose of study drug.

\* All reactivations of hepatitis B are to be recorded as Grade 3 (CTCAE v 4.0 Infections and Infestations: Hepatitis Viral), unless considered life threatening by the investigator; in which case they should be recorded as Grade 4 (CTCAE 4.0 Infections and Infestations: Hepatitis Viral). Date of viral reactivation is the date on which **both** DNA and ALT criteria were met (e.g. for a patient who was HBV-DNA positive on 01-JAN-10 and whose ALT reached  $\geq 5 \times$  ULN on 01-APR-10, the date of viral reactivation is 01-APR-10).

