### 7.1 Good Medical Practice

The following tests (and/or assessments) are recommended within 28 days prior to registration in accordance with Good Medical Practice. Results of these tests do not determine eligibility and minor deviations from normal limits would be acceptable if they do not affect patient safety in the clinical judgment of the treating physician. If there are significant deviations in these tests/assessments that could impact on patient safety, it is highly recommended that the registering investigator discuss the patient with the Study Chair prior to registering.

- a. Patients should not have an uncontrolled intercurrent illness including, but not limited to active bleeding diathesis, uncontrolled infection/disorders, nonmalignant medical illnesses that are uncontrolled or whose control may be jeopardized by the treatment with the study therapy, or psychiatric illness/social situations that would limit compliance with study requirements.
- b. Testing for hepatitis B viral load and serologic markers: HBV-DNA, HBsAg, HBs Ab, and HBc Ab should be performed at screening for all patients with the following risk factors (see [Section 7.3](#) and [8.6](#)):
  - Patients who currently live in (or have lived in) Asia, Africa, Central and South America, Eastern Europe, Spain, Portugal, and Greece.
  - known or suspected past hepatitis B infection,
  - blood transfusion(s) prior to 1990,
  - current or prior IV drug users,
  - current or prior dialysis,
  - current or prior high-risk sexual activity,
  - body piercing (other than ear piercing) or tattoos,
  - mother known to have hepatitis B
  - history suggestive of hepatitis B infection, e.g., dark urine, jaundice, right upper quadrant pain.
  - Additional patients at the discretion of the investigator
  - household contact with hepatitis B infected patient(s),

Testing for hepatitis C should be performed using quantitative RNA-PCR at screening for patients with the following risk factors (see [Section 8.6](#)):

- known or suspected past hepatitis C infection (including patients with past interferon 'curative' treatment),
  - blood transfusions prior to 1990,
  - current or prior IV drug users,
  - current or prior dialysis,
  - household contact of hepatitis C infected patient(s),
  - current or prior high-risk sexual activity,
  - body piercing other than ear piercing or tattoos,
  - Additional patients at the discretion of the investigators

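### Section 8.6, Table 2, row 1 counts the 1-log HBV-DNA rise from the screening value, so a patient whom prophylaxis suppresses by more than 1 log, but not to unmeasurable, can rebound 100-fold with raised ALT and not count as a reactivation

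*Combined protocol and SAP*

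**What the plan says.** All references are to the combined protocol and SAP.

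- **When baseline is measured.** Section 7.1b: "HBV-DNA, HBsAg, HBs Ab, and HBc Ab should be performed at screening for all patients with the following risk factors". The introduction to Table 1 in Section 8.6 sets monitoring and prophylaxis "according to the baseline results of viral load and serologic markers testing".
- **What follows a positive result.** Table 1, for patients positive for HBV-DNA or HBsAg: "Prophylaxis treatment should be started 1-2 weeks prior to first dose of study drug", then "Monitor HBV-DNA approximately every 4-6 weeks". Section 7.3 strongly recommends this prophylaxis without requiring it, and continues it through the study. The Section 9.0 calendar shows on-study HBV-DNA tests from Cycle 2.
- **The definition.** Table 2, row 1, has two alternative DNA criteria. One is "Increase of 1 log in HBV-DNA relative to baseline HBV-DNA value"; the other is new appearance of measurable DNA. Either must be joined by ALT at 5 x ULN.
- **The action.** "Start a second antiviral AND Interrupt study drug administration until resolution". Resolution requires ALT at Grade 1 or below (or at baseline, if that was higher) "and ≤ baseline HBV-DNA levels".
- **The record.** Table 2 footnote: "All reactivations of hepatitis B are to be recorded as Grade 3", under the Hepatitis Viral term, or Grade 4 if life-threatening.

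Baseline is not formally defined, but these sections support only the screening value. No section moves the reference to a value obtained on the antiviral.

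**The concern.** The row's action is a second antiviral, so it presumes a patient already on a first. Its trigger is nevertheless measured from a value taken before that first antiviral began. The better prophylaxis works without clearing DNA entirely, the larger the rebound must be before the definition is met. ALT cannot make up the difference, because the two conditions are joined by AND.

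The result is uneven. Take two patients who screen at 10^6 and later have ALT at 6 x ULN. One is suppressed to unmeasurable and becomes barely measurable again; in the ordinary meaning of new appearance this is a reactivation. The other is suppressed to 10^3 and rebounds to 10^5; this is not, although the viral load is higher and the 100-fold rise is documented.

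At stake are the table's specific instruction on antiviral treatment and the correct name for the event in the toxicity data.

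**Working it through.** The plan gives no figure to reproduce; the check is log10 arithmetic on the definition.

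**Inputs.** S = screening log10 HBV-DNA (Section 7.1b). N = S − k = level on the antiviral, still measurable. The DNA threshold in Table 2 is S + 1. The documents give no value for k, so a range is shown. The 100-fold (2-log) rebound is illustrative.

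**Rise needed under Table 2.** (S + 1) − N = k + 1 logs.

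**Level after a 100-fold rebound.** N + 2 = S + 2 − k. This reaches S + 1 only if k ≤ 1.

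**DNA part of the restart condition.** DNA must be at or below S. After a 100-fold rebound that is already true when 2 − k ≤ 0, that is, k ≥ 2.

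| k (logs) | Rise needed now | Level after 100-fold rebound | DNA criterion met now? | Already at or below screening? |
|---|---|---|---|---|
| 0.5 | 10^1.5 = 32-fold | S + 1.5 | yes | no |
| 1 | 10^2 = 100-fold | S + 1 | yes (just) | no |
| 1.5 | 10^2.5 = 316-fold | S + 0.5 | no | no |
| 2 | 10^3 = 1,000-fold | S | no | yes |
| 3 | 10^4 = 10,000-fold | S − 1 | no | yes |

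The alternative DNA criterion does not help in these rows, because DNA never became unmeasurable.

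**Example (k = 3).** Screening 10^6, on antiviral 10^3, later 10^5 with ALT 6 x ULN. Table 2 needs 10^7, so this is not a reactivation.

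**Proposed reference.** Threshold = min(S, N) + 1. In the example this is 10^4, so 10^5 counts. A 10-fold rise suffices at every k. Because min(S, N) + 1 is never above S + 1, no event that meets the present definition is lost.

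**Effect on reported rates.** The number of such patients is not given. If 1 to 5 patients in an arm of 732 (Section 11.3) were classified differently, the rate for that one term would move by 1/732 = 0.14 to 5/732 = 0.68 percentage points. The plan's stated worst-case precision is 3.7 points.

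**The case against.** The strongest reply is that the patient is managed anyway. A reader might infer from Table 2 that a missed reactivation leaves the patient on everolimus. The documents do not support that. If ALT at 5 x ULN is Grade 3 (an assumption, since the CTCAE scale is not printed), Section 8.4 holds the drug to Grade 1 or below and resumes it one level lower. Section 8.2e removes the patient after a hold of more than 28 days. These match Table 2. At the lowest dose Section 8.4 is stricter, because the next level in Section 8.3 is discontinuation, whereas Table 2 restarts at the same dose. Section 8.5 names hepatitis B reactivation and calls for prompt treatment, Section 7.3 permits any therapy the patient needs, and the physician has the HBV-DNA results. All of this stands.

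A reader might also infer that the HBV-DNA restart condition is lost and would be restored by a new reference. After a 100-fold rebound this holds only for k between 1 and 2. From k = 2 up, including the k = 3 example, DNA is already at or below screening, so that condition would not bind.

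Nor does the event vanish from the safety data. On the same grading assumption, the ALT rise is itself a Grade 3 event on the Adverse Event Form (Section 14.4c). Only the term changes.

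Finally, a screening reference favours specificity. The lowest of repeated measurements carries downward noise, and raised ALT is a listed everolimus effect (Section 3.1c). This is a real cost, limited by keeping the ALT condition.

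The dated example in the Table 2 footnote does not rescue the definition. It shows how to date an event and does not change the reference for the 1-log rise.

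**Conclusion.** The point holds in a narrow form. For a patient who is DNA-positive and untreated at screening, takes the recommended prophylaxis, and is suppressed by more than 1 log but stays measurable, a 100-fold rebound with ALT at 5 x ULN falls outside the definition. Patients already on a stable antiviral at screening, those who do not take prophylaxis, and those suppressed to unmeasurable (on the ordinary reading of new appearance) are not affected.

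Given the assumption that ALT at 5 x ULN is Grade 3, the loss is the explicit prompt for a second antiviral and the Hepatitis Viral classification. The documents support no claim of uncontrolled everolimus exposure or of bias between arms: the same definition applies to both blinded arms. The primary analysis is unaffected. The group needs several conditions at once and is likely very small.

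The point matters only for patients still being dosed, and there may be none. The December 2020 update in Section 11.2 allows six years of follow-up after last accrual, with final analysis by March 2022. Counting back puts last accrual at about March 2016, and 54 weeks of treatment would then have ended in about spring 2017. The documents do not state the last dosing date. This is a cheap improvement to consider, not a flaw in the trial's conclusions.

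**What to change.** In Table 2, row 1:

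- For a patient on an antiviral, count the 1-log rise from the lower of the screening value and the lowest HBV-DNA already obtained on the antiviral. Keep the screening value if the patient is not on an antiviral or has no on-antiviral result.
- State that new appearance of measurable DNA includes re-appearance after an unmeasurable result.
- Leave the ALT criterion, the resolution target and the sampling schedule as they are.

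The cost is wording in one table row; the 4-6 weekly tests already supply the values. The downside is that a few drug-related ALT rises that coincide with a 10-fold DNA change may lead to a second antiviral that was not needed.

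Retrospective reclassification is not advised: the submission list in Section 14.4 names no HBV-DNA report, so the central data may not support it.

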### Monitoring for Hepatitis C

The following two categories of patients should be monitored every 4-6 weeks for HCV reactivation:

- Patients with detectable HCV RNA-PCR test at baseline.
- Patients known to have a history of HCV infection, despite a negative viral load test at baseline (including those that were treated and are considered 'cured')

For definition of hepatitis C reactivation and the management guidelines, see [Table 3](#) Guidelines for management of hepatitis C.

**Table 3 Guidelines for management of hepatitis C**

HCV reactivation*	
For patients with baseline results: Detectable HCV-RNA,  reactivation is defined as: ALT elevation x 5 ULN	Discontinue study drug
For patients with baseline results: Knowledge of past hepatitis C infection with no detectable HCV- RNA,  reactivation is defined as: New appearance of detectable HCV- RNA	Discontinue study drug

\* All reactivations of hepatitis C are to be recorded as Grade 3 (CTCAE 4.0 Infections and Infestations: Hepatitis Viral), unless considered life threatening by the investigator; in which case they should be recorded as Grade 4 (CTCAE 4.0 Infections and Infestations: Hepatitis Viral).

#### 8.7 Emergency Unblinding

For emergency unblinding guidelines see [Section 18.2](#).

#### 8.9 Adverse Event Reporting

Toxicities (including suspected reactions) that meet the expedited reporting criteria as outlined in [Section 16.0](#) of the protocol must be reported to the Operations Office, Study Chair, the NCI via CTEP-AERS, and to the IRB per local IRB requirements.

9.0 STUDY CALENDAR

√

REQUIRED STUDIES	PRE STUDY	Cycle 1						Cycle 2		Cycle 3 §		Off Treat F/U Prior to Recurrence	Recurrence	Off Treat F/U After Recurrence
		WK 1	WK 2	WK 3	WK 4	WK 5	WK 6	WK 7 ----->12	WK	WK 13 ----->18	WK			
PHYSICAL														
History and Physical Exam	X*	XЯ			X			X		X		X	X	X
Hepatitis B/C Screening †	X													
Weight and Performance Status	X	XЯ						X		X				
Recurrence Assessment ¶ Ж											X	X¶	X	
Toxicity Notation Ω		X	X	X	X	X	X	X		X				
Review Intake Calendar								X		X				
LABORATORY														
WBC/Differential /Platelets	X							X		X				
Hemoglobin	X							X		X				
Bilirubin	X							X		X				
SGOT and SGPT	X							X		X				
Serum Creatinine or Calculated Creatinine Clearance	X							X		X				
Alkaline Phosphatase	X							X		X				
Fasting Glucose, Cholesterol and Triglycerides	X							X		X				
HBV DNA or HCV RNA-PCR Δ								X		X				

Study Calendar continued on next page. Click here for [footnotes](#).

√

REQUIRED STUDIES	PRE STUDY	Cycle 1						Cycle 2		Cycle 3 §		Off Treat F/U Prior to Recurrence	Recurrence	Off Treat F/U After Recurrence
		WK 1	WK 2	WK 3	WK 4	WK 5	WK 6	WK 7 ----->12	WK 13 ----->18	WK	WK			
SPECIMEN SUBMISSION ¶														
Archived Tumor Specimen	X													
Buffy Coat and Plasma Specimens	X							X		X		X	X	
Whole Blood for Trough Levels	X							X		X		X		
X-RAYS AND SCANS														
CT Scan of Chest/Abdomen/Pelvis £ ¶	X										X £ ¶	X	X	
Bone Scan ¶	X¶											X¶		
TREATMENT (see Section 7.0 for details)														
Everolimus/Placebo		X ----->X												

Click here for [footnotes](#).

FOOTNOTES:

**NOTE: Forms are found in [Section 18.0](#). Forms submission guidelines may be found in [Section 14.0](#).**

- \* Physical exam and medical history must be completed within 28 day prior to registration (see [Section 5.3a](#)).
- Δ Only for patients with positive HBV or HCV studies at baseline (see [Section 8.6](#)).
- † An assessment of Hepatitis B/C medical history and risk factors must be done at screening (see [Section 5.3h](#)). Patients with risk factors for Hepatitis B should undergo HBV DNA, HBsAg, HBsAb, and HBcAb testing (see [Sections 7.1, 7.3](#) and [8.6](#)). Patients with risk factors for Hepatitis C infection should undergo HCV RNA-PCR testing (see [Sections 7.1](#) and [8.6](#)).
- § Protocol treatment will continue at the same intervals indicated for Cycle 3 for a maximum of 9 cycles (54 weeks) or until the patient has met any of the criteria listed in [Section 7.6](#).
- √ After recurrence, follow-up will occur (with lab tests and scans performed at the discretion of the treating physician) every 6 months for the first two years and then yearly thereafter until 10 years after registration.
- £ CT scans of the chest must also be assessed for radiographic evidence of pneumonitis (see [Section 8.4c](#)).
- Ж Scan (CT scan of the chest, abdomen and pelvis with IV and oral contrast; CT scan of chest without contrast and MRI of abd/pelvis with gadolinium) and recurrence assessment must be performed every 4 months (18 weeks) during Year 1 (regardless of early protocol treatment discontinuation), every 6 months for Years 2 and 3, and yearly thereafter until recurrence, death, or 10 years after registration whichever comes first.  
The surveillance imaging therapy intervals prescribed here are considered standard of care by expert consensus (SWOG Genitourinary Committee) based on the high risk of cancer recurrence in the patients enrolled in this study. Non-contrast CT of the chest/abdomen/pelvis should only be used for surveillance imaging if, in the opinion of the investigator, it is in the best medical interest of the patient to not receive IV contrast of any form.  
NOTE: PET/CT is not an acceptable imaging alternative.
- ¥ See [Section 15.0](#). If patient has consented to banking for the translational medicine component, it is very important to obtain whole blood for trough levels and buffy coat and plasma specimens from any patient that is being removed from protocol treatment, regardless of the time point. DO NOT COLLECT SPECIMENS AT EACH VISIT DURING FOLLOW-UP. Additionally, specimens for buffy coat and plasma specimens should be collected at disease recurrence. **Specimens must be drawn prior to daily dose of study drug.**
- Ω Once everolimus treatment has been initiated, weekly toxicity assessments are required during the first cycle. Toxicity assessments during the first cycle may be performed via a phone call during weeks when a physical exam is not required.
- Н Bone scan recommended if patient has rising alkaline phosphatase or bone pain.
- Я If prestudy history and physical exam, weight and performance status are obtained within 28 days prior to registration, they do not need to be repeated for Cycle 1, Day 1.
- ¶ If patient is taken off protocol treatment due to toxicity or other reason besides recurrence, they must continue to be followed for recurrence with physical exams and scans every 4 months (18 weeks) during Year 1 (regardless of early protocol treatment discontinuation), every 6 months for Years 2 and 3, and yearly thereafter until recurrence, death, or 10 years after registration whichever comes first.

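### The study calendar's footnote on HCV-RNA testing leaves out patients with past hepatitis C and a negative baseline load, whom Section 8.6 lists for monitoring

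*Combined protocol and SAP*

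**What the plan says.** Four parts of the protocol bear on this.

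- **Section 9.0, calendar.** The row "HBV DNA or HCV RNA-PCR Δ" is marked at the start of Cycle 2 (week 7) and Cycle 3 (week 13). It is not marked pre-study or in Cycle 1. Footnote § carries the Cycle 3 pattern on to a maximum of nine six-week cycles.
- **Section 9.0, footnote Δ.** This row applies "Only for patients with positive HBV or HCV studies at baseline". The footnote ends with a cross-reference to Section 8.6.
- **Section 8.6, hepatitis C monitoring.** Two categories "should be monitored every 4-6 weeks for HCV reactivation". The first is "Patients with detectable HCV RNA-PCR test at baseline". The second is "Patients known to have a history of HCV infection, despite a negative viral load test at baseline", and it expressly takes in patients who were treated and are regarded as cured.
- **Section 8.6, Table 3.** For the group described as "Knowledge of past hepatitis C infection with no detectable HCV- RNA", reactivation is the new appearance of detectable HCV-RNA, and the listed action is to discontinue study drug.

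On baseline testing, Section 7.1b says "Testing for hepatitis C should be performed using quantitative RNA-PCR at screening" for patients with risk factors, and known or suspected past infection is one of those factors. Footnote † of the calendar repeats this: "Patients with risk factors for Hepatitis C infection should undergo HCV RNA-PCR testing".

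**The concern.** The calendar and Section 8.6 describe different populations for the same test. Section 8.6 includes a group defined by a negative baseline RNA result, while the calendar confines testing to patients with a positive baseline study. A site that builds its visit schedule from the calendar wording could reasonably order no on-treatment RNA tests for patients with past, RNA-negative hepatitis C.

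The test is what makes a Table 3 rule work. For this group the rule has no other input, and it carries a treatment consequence. Section 8.5 describes everolimus as immunosuppressive and notes viral infections in patients taking it. Table 3 also says how every HCV reactivation is to be graded and recorded, so an undetected one would be missing from the adverse event record as well.

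**Working it through.** The plan states no figure on this point, so there is none to reproduce. The check compares the texts and then sizes the gap.

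**Step 1. Can the second Section 8.6 group satisfy footnote Δ?** The baseline HCV test is RNA-PCR in Section 7.1b and again in footnote †. Section 5.3h requires HCV testing for patients with a relevant history, but it sends the reader to Section 9.0 for the test, which is again RNA-PCR. No HCV antibody test is named anywhere. The second group is defined by a negative result on the only named HCV study, so it has no positive HCV study at baseline.

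| Group | Section 8.6 | Footnote Δ wording |
|---|---|---|
| HCV RNA detectable at baseline | monitor | included |
| Past HCV, RNA negative at baseline | monitor | excluded |

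**Step 2. Does another provision fill the gap?** For hepatitis B, yes: antibody-positive, DNA-negative patients do have a positive baseline study, and Section 7.3 separately sends patients with positive HBV antibodies for HBV-DNA testing on the visit schedule. Section 7.3 has no counterpart for hepatitis C. The gap is specific to HCV.

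**Step 3. Could the liver enzymes stand in?** SGOT and SGPT are scheduled every cycle from Cycle 2. In Table 3 the ALT criterion belongs to patients with detectable RNA at baseline. For the RNA-negative group the criterion is RNA alone, so an enzyme result cannot meet it.

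**Step 4. How many tests per patient?** The row starts at Cycle 2 and runs to Cycle 9 at most: 9 − 1 = 8 scheduled tests, and fewer for anyone who stops treatment early.

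**Step 5. How many patients?** The documents do not give the prevalence of past, RNA-negative HCV. Assume 0.5% to 2% of the 1,537 projected patients (Section 11.2):

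- 0.005 × 1,537 = 7.7, about 8
- 0.02 × 1,537 = 30.7, about 31
- with two equal arms, on everolimus: 7.7 / 2 = 3.8, about 4; and 30.7 / 2 = 15.4, about 15

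**Step 6. Is treatment likely still under way?** The December 2020 update in Section 11.2 plans six years of follow-up after the last accrual, with the final analysis expected in March 2022 at the latest. Six years before March 2022 is March 2016. With 54 weeks of treatment (Section 7.2), the last patients would finish around spring 2017. On that timeline treatment had ended before the update, although the documents do not say so directly.

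**The case against.** The strongest answer is that footnote Δ does not stand alone. It points to Section 8.6, which lists both groups explicitly, and a site that follows the pointer would test these patients. This stands, and it limits the consequence. A reader might infer that the patients would go untested and that their stopping rule could not operate. The documents do not support that: it holds only where a site acts on the calendar wording and does not follow, or does not give precedence to, the cited section. Nothing in the protocol says which of the two texts governs. The cross-reference therefore makes a missed test less likely but does not remove the contradiction.

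A second answer is that the protocol uses the word positive loosely. Table 1 is headed as dealing with positive baseline hepatitis B results, yet it has a column for patients negative for HBV-DNA, HBsAg and HBc Ab. Section 5.3h speaks of a positive medical history. So the footnote may be shorthand for any relevant hepatitis status. That is a possible reading, but the footnote refers to studies at baseline, and Section 5.3h treats history as the reason for testing, not as a test result. The wording remains ambiguous at best.

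Third, liver monitoring continues. Enzymes are checked each cycle for every patient, and Section 8.4 has its own rules for non-hematological toxicity. This stands: it would be wrong to say that these patients have no liver surveillance. What could be missed is a reactivation shown by RNA alone.

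Fourth, the practical value now is limited if treatment has finished. This also stands, and it shapes the fix.

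**Conclusion.** The point holds as an internal inconsistency in safety monitoring. On its wording, footnote Δ excludes a group that Section 8.6 lists for HCV monitoring and for which Table 3 sets an RNA-only criterion. The finding that the texts conflict rests on the text alone and needs no assumption.

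The consequence is conditional. Where the calendar wording is followed, up to eight scheduled RNA tests per patient may be missed and a reactivation may go undetected. The patient numbers (about 8-31 over both arms, about 4-15 on everolimus) rest wholly on the assumed 0.5-2% prevalence and on equal arms, and only the everolimus share is exposed to the drug. Sample size, power and alpha are untouched.

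This review takes no view on which monitoring list or stopping rule is right, only that the passages disagree and must be reconciled.

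**What to change.** Reconcile footnote Δ in Section 9.0 with the HCV monitoring list and Table 3 in Section 8.6, so that all three name the same patient groups for HCV-RNA monitoring. The sponsor should decide which groups those are.

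The cost is the rewording of one footnote or of the matching text in Section 8.6. If the Section 8.6 list is kept, no tests are added beyond those it already calls for.

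If protocol treatment is complete, rewording changes no patient's testing. The useful step is then to identify patients with known past HCV and a negative baseline load, check whether on-treatment HCV-RNA tests were done, and note any gap when the adverse event data are reported.
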